6.12.1. Extent of Exposure

The exposure will be calculated as:

Date of last study visit during the treatment period – Date of first dose for the treatment period of Study AMAH+1 day

Overall exposure will be summarized in total patient years (PY), derived in the following manner:

$$\text{Exposure in PY} = \text{Sum of duration of exposure in days (for all patients in treatment group)} / 365.25.$$

Total PY of exposure will be reported. Descriptive statistics will be provided for patient-weeks of exposure and the frequency of patients falling into different exposure ranges will be summarized:

- >0; ≥ 24 weeks; ≥ 48 weeks; ≥ 72 weeks; ≥ 96 weeks; ≥ 120 weeks; ≥ 152 weeks; ≥ 184 weeks; ≥ 208 weeks
- >0 to <24 weeks; ≥ 24 weeks to <48 weeks; ≥ 48 weeks to <72 weeks; ≥ 72 weeks to <96; ≥ 96 weeks to <120; ≥ 120 weeks to <152; ≥ 152 weeks to <184 weeks; ≥ 184 weeks to <208 weeks; ≥ 208 weeks.

Additional exposure ranges may be considered, if necessary. No p-values will be reported in these tables as they are intended to describe the study populations, rather than test hypotheses about them.

A by-patient listing of assigned treatments will be provided.

6.12.2. Immunogenicity

Immunogenicity will be evaluated cumulatively, using data both from the patient's originating study and from the present study. Baseline for ADA assessment will be the baseline ADA assessment from the originating study, and postbaseline will be time after initiation of mirikizumab.

An individual sample is potentially examined multiple times in a hierarchical procedure to produce a sample anti-drug antibodies (ADA) assay result and potentially a sample neutralizing anti-drug antibodies (NAb) assay result. A patient has treatment-emergent anti-drug antibodies (TE-ADA) when ADA are induced or boosted by exposure to study drug; i.e., when at least one postbaseline ADA sample has a 4-fold increase in titer, compared to baseline (if ADA were present at baseline) or has a titer 2-fold greater than the minimum required dilution of 1:10 (if no ADA were present at baseline).

Compound level safety standards will be followed in the analyses of immunogenicity. The summary of TE ADA and neutralizing antibody (NAb) status will be produced for the ITT population (including originating studies and Study AMAH).

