Most patients will enter Study AMAH at the last visit of a qualifying study period of the originator studies. All patients must enter Study AMAH within 12 weeks of their final visit in these periods or they will become ineligible. Patients in the secukinumab treatment group of Study AMAJ will be eligible to enter Study AMAH; such patients will receive mirikizumab for the first time in Study AMAH.

Treatment Period:

All patients participating in Study AMAH will receive subcutaneous (SC) administration of mirikizumab every 8 weeks (Q8W). The dose used in Study AMAH will depend on the treatment that the patients were receiving during the qualifying period of the originator study. For all treatment groups in Study AMAH, dosing begins at Visit 1 and continues to Week 208.

- Patients entering from Study AMAJ or Study AMAK who received mirikizumab during the qualifying period will continue to receive the dose they were receiving (either 250 mg mirikizumab Q8W SC or 125 mg mirikizumab Q8W SC). Patients entering from Study AMAJ or Study AMAK who were receiving secukinumab or placebo, respectively, during the qualifying period will receive 250 mg mirikizumab Q8W SC.
- Patients entering from Study AMBK will receive 250 mg mirikizumab Q8W SC.
- Patients entering from Study AMAF whose last treatment was 300 mg mirikizumab, on either the fixed Q8W dosing regimen or on the as-needed (PRN) regimen, will start 250 mg mirikizumab Q8W SC in Study AMAH. Patients entering from Study AMAF whose last treatment was either 30 mg or 100 mg mirikizumab on a PRN regimen will start 125 mg mirikizumab Q8W SC in Study AMAH.
- After Study AMAH dosing is no longer blinded, patients who in the opinion of the investigator have experienced significant clinically meaningful loss of efficacy during study participation may be increased from 125 mg mirikizumab Q8W to 250 mg mirikizumab Q8W if it is determined by the patient and the investigator that the patient might benefit from additional study drug in order to maintain satisfactory disease

control. All patients who increase dosing to 250 mg mirikizumab Q8W will remain on this dose until completion of the study or early discontinuation.

Post-Treatment Follow-up Period (12 weeks):

All patients, whether they discontinue early for any reason or else complete study treatment, will enter the 12-week Post-Treatment Follow-Up Period.

Number of Patients:

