- j These assessments should be completed before administration of IP; before the patient's clinical examination; before the patient receives any tests or results; and before the patient's health, health data, or emotions are discussed.
- k Unscheduled blood chemistry and hematology panels may be performed at the discretion of the investigator. See [Appendix 2](#), for details.

- ^l Any enrolled patient who is HBcAb+ in the originator trial will undergo monitoring of HBV DNA with HBV DNA testing (see Section 9.4.5.3). Any patient with a positive HBV DNA test at any time must be discontinued from the study and receive appropriate follow-up medical care, including consideration for antiviral therapy.
- ^m Any enrolled patient with a history of HCV infection (tested positive for HCV antibody in the originator study) who develops elevated ALT >3xULN will be tested for HCV RNA (see Section 9.4.5.4). Any patient with a positive HCV RNA test must be discontinued from the study and receive appropriate follow-up medical care, including consideration for antiviral therapy.
- ⁿ Immunogenicity samples should be collected prior to dosing on visits when mirikizumab is administered. A sample will be obtained at unscheduled visits if a patient develops an acute hypersensitivity event after administration of IP (see Section 7.8.2.1).
- ^o Sample from last visit of originator study should be used. If no sample <4 weeks old is available, then a baseline sample should be collected in this study.
- ^p Scheduled pharmacokinetic samples are taken as an aliquot from the immunogenicity sample. Unscheduled pharmacokinetic samples, obtained if a patient develops an acute hypersensitivity event after administration of IP (see Section 7.8.2.1), will be collected in a separate tube. To be performed only on women of child-bearing potential. Between visits, urine pregnancy tests are to be performed monthly at home.
- ^r If a patient discontinues IP early, the patient will complete the ETV and then enter the Post-Treatment Follow-up Period (Visit 801 and Visit 802).
- ^s Urinalysis assessed only for early termination due to an adverse event for which urinalysis is clinically indicated.

3. Introduction

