5.1.1. Qualifying Period

Patients who qualify for Study AMAH may enter directly into the study upon the last visit of a qualifying study treatment period (LVTP) of the originator study. For most patients, Week 52 of the originating study (AMAJ and AMAK) will be the LVTP and will coincide with Week 0 (Visit 1) for Study AMAH. Similar alignment will occur for other originator studies, that is, Visit 1 of Study AMAH to coincide with the LVTP in AMAF or AMBK. The qualifying study treatment periods of the originator studies are as follows:

- AMAJ, AMAK, AMAF: Blinded Maintenance Period
- AMBK: Treatment Period

Study investigator(s) will review patient data from the LVTP in the respective originating study to determine if the patient meets all inclusion and none of the exclusion criteria to qualify for participation in Study AMAH.

If, at LVTP of the originating study, a patient is not able to enter Study AMAH (for example, due to unresolved safety concerns), the patient will be evaluated in the originating study for up to 12 weeks beyond the LVTP (that is, in a post-treatment follow up period) to determine whether treatment with investigational product can resume in Study AMAH. If, in the opinion of the investigator, starting or restarting treatment with mirikizumab does not pose an unacceptable risk, the patient can begin participation in Study AMAH, that is, have Visit 1 in Study AMAH. Eligible patients must enter Study AMAH within 12 weeks of the LVTP of originating study or they will become ineligible.

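### For AMAJ secukinumab patients the ADA baseline predates the first mirikizumab dose by 52 to 64 weeks, so treatment-emergent ADA can be misclassified in either direction

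*SAP*

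**What the plan says.** SAP Section 6.12.2 and protocol Section 10.3.6 carry the same sentence: "Baseline for ADA assessment will be the baseline ADA assessment from the originating study, and postbaseline will be time after initiation of mirikizumab". Neither makes an exception for any cohort.

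SAP Section 6.12.2 describes TE-ADA as antibodies that study drug brings on or increases. It then gives two working thresholds:

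- ADA present at baseline: "at least one postbaseline ADA sample has a 4-fold increase in titer, compared to baseline (if ADA were present at baseline").
- ADA absent at baseline: a sample that "has a titer 2-fold greater than the minimum required dilution of 1:10 (if no ADA were present at baseline").

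Of the AMAJ secukinumab group, the protocol (Synopsis and Section 6) says that "such patients will receive mirikizumab for the first time in Study AMAH". SAP Section 6.1.1 makes these patients Cohort 3 and reports safety analyses by cohort.

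On timing, protocol Section 5.1.1 says: "For most patients, Week 52 of the originating study (AMAJ and AMAK) will be the LVTP and will coincide with Week 0 (Visit 1"). It adds: "Eligible patients must enter Study AMAH within 12 weeks of the LVTP of originating study or they will become ineligible".

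The protocol's Schedule of Activities lists an immunogenicity sample at Visit 1. Footnote o takes the last originator-study sample for this, and continues: "If no sample <4 weeks old is available, then a baseline sample should be collected in this study". Footnote n fixes the order of sampling and dosing: "Immunogenicity samples should be collected prior to dosing on visits when mirikizumab is administered".

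**The concern.** The rule ties the start of the post-baseline period to mirikizumab but does not tie the baseline to it. For a patient who started mirikizumab at originator baseline the two points coincide and nothing is lost. For Cohort 3 they are about a year apart, and no mirikizumab was given in between. Any change in anti-mirikizumab titre over that year enters the comparison as if mirikizumab had caused it, which is not what the SAP says TE-ADA means.

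The sample that would separate the two is the pre-dose one at Visit 1. Under the stated definitions it is not the baseline, because it does not come from the start of AMAJ. It is not post-baseline either, because mirikizumab has not begun.

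TE-ADA and neutralizing-antibody status define the exploratory relationships of ADA with efficacy, adverse events and pharmacokinetics, so a wrong label would carry into those. Cohort 3 is also the only cohort that the documents say is new to mirikizumab on entry.

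**Working it through.** **1. The plan's own figure.** The only planning number is expected enrolment (protocol Section 10.1, SAP Section 5.2). Originator sizes sum to 205 + 1440 + 500 + 300 = 2445. Completion times continuation is 0.8 × 0.8 = 0.64 to 0.9 × 0.9 = 0.81. This gives 2445 × 0.64 = 1565 and 2445 × 0.81 = 1980, which agrees with the stated 1600 to 2000. It is used below only as a denominator.

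**2. Age of the comparator in Cohort 3.** The AMAJ baseline is taken as AMAJ Week 0 (an assumption, since the AMAJ protocol is not among the documents).

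- Usual entry: 52 weeks × 7 = 364 days, or 364 / 365.25 = 1.00 year.
- Latest entry: 52 + 12 = 64 weeks × 7 = 448 days, or 448 / 365.25 = 1.23 years.
- With the Visit 1 sample, or the originator sample used in its place under footnote o: less than 4 weeks.

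**3. The rule applied to titres.** With ADA present at baseline, TE-ADA needs a post-dose titre of at least 4 × baseline. With ADA absent it needs at least 2 × 1:10, read here as 1:20 or higher.

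| AMAJ baseline | Visit 1, pre-dose | Post-dose | SAP rule | Visit 1 as baseline |
|---|---|---|---|---|
| Not detected | 1:20 | 1:20 | TE-ADA (1:20 needed) | Not TE-ADA (1:80 needed) |
| 1:40 | Not detected | 1:80 | Not TE-ADA (1:160 needed) | TE-ADA (1:20 needed) |

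In the first row nothing changed after mirikizumab, yet the patient counts. In the second, antibodies appeared after mirikizumab, yet the patient does not.

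**4. A grid of cases.** The values used were:

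- AMAJ baseline: not detected, 1:20, 1:40.
- Visit 1: not detected, 1:10, 1:20, 1:40, 1:80.
- Post-dose: not detected, 1:20, 1:40, 1:80, 1:160.

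That makes 3 × 5 × 5 = 75 combinations. The two baselines disagree in 23. In 14 the SAP rule says TE-ADA and the Visit 1 baseline does not; in 9 it is the reverse. Every disagreement has a different value at AMAJ baseline and Visit 1. Where the two values are equal there are none. The 75 are not weighted by how often they occur, so 23 of 75 is not a rate.

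**5. Possible size.** The documents give neither the size of Cohort 3 nor the rate of ADA change without mirikizumab. Assume 100 to 400 patients, and assume that 0% to 5% become positive at 1:20 or higher before exposure and stay so, with no four-fold rise over Visit 1 after dosing.

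- Falsely labelled: from 0 up to 100 × 0.05 = 5, or up to 400 × 0.05 = 20.
- Share of Cohort 3: 0% to 5%.
- Share of all enrolled patients: at most 20 / 2000 = 1.0% to 20 / 1600 = 1.25%.

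Cases missed in the opposite direction were not counted, because nothing in the documents supports a range for them.

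**The case against.** The strongest reply is that a possibility has been shown, not an occurrence. No section says that anti-mirikizumab titres move in patients not given mirikizumab. Protocol Section 9.4.4 requires Tier 2 confirmation before a sample is reported as detected and titred, which should remove some non-specific reactivity. That stands, and it is why the range above starts at zero. It does not alter the comparator once a sample is confirmed.

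Second, the SAP already keeps samples taken on secukinumab from counting as treatment-emergent, since post-baseline begins with mirikizumab. This is true, and a reader should not infer otherwise. It leaves the baseline itself a year old.

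Third, SAP Section 6.12.2 defers to compound-level safety standards, which may hold a rule for late starters. Their content is not available. If they do hold one, it conflicts with the explicit baseline sentence, and that sentence still needs correcting.

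Fourth, footnote o might be read as showing that Visit 1 was meant to be the TE-ADA baseline. The documents do not support that. The footnote covers all entrants, including those long on mirikizumab, and the amendment summary gives continuity of sampling as the reason for adding the sample. The sample also supplies the paired drug concentration. It has a purpose, but no part in the TE-ADA rule.

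**Conclusion.** The gap is real. For Cohort 3 the stated rule does not measure what the SAP says TE-ADA is, and errors can run both ways. They are confined to patients whose ADA status or titre changed between AMAJ baseline and the first mirikizumab dose.

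A reader might go further and infer that TE-ADA is in fact misclassified in this cohort. The documents give no rate of pre-exposure change, so the range of 0 to 20 false labels rests wholly on the assumed cohort size, conversion rate and persistence.

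Nor do the documents support a large relative inflation of the TE-ADA rate. Setting 1% to 5% false labels against a true rate of 10% would suggest 10% to 50%. Those inputs are assumed and exclude zero, and the sum ignores the missed cases. It also counts some patients who would qualify anyway: if the two are independent, 0.9 × (1% to 5%) = 0.9 to 4.5 points, or 9% to 45%.

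The affected output is the descriptive TE-ADA and neutralizing-antibody summary and the exploratory ADA relationships. The primary and secondary endpoints do not depend on ADA status, and the study tests no hypotheses.

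**What to change.** In SAP Section 6.12.2, define ADA baseline as the last ADA sample before the patient's first mirikizumab dose in the program. For Cohort 3 this is the AMAH Visit 1 sample, or the originator sample used under footnote o. Patients who started mirikizumab at originator baseline keep their present baseline. Optionally, show the result with the originating-study baseline as a sensitivity summary.

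The cost for Cohort 3 is a SAP revision and a change to one derivation. The samples are already scheduled, and protocol Section 9.4.4 sends every sample through screening. Protocol Section 10.3.1 and SAP Section 6.1 require a protocol amendment only when a principal feature changes. A note in the clinical study report explaining the departure from protocol Section 10.3.6 therefore appears sufficient.

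The wording would also cover any AMAK placebo patient who had never received mirikizumab. The documents do not say whether such patients exist, so originator dosing dates and ADA sampling would have to be checked for them.

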Immunogenicity for mirikizumab ⁿ	X ^o	X	X	X			X			X			X	
Serum for mirikizumab concentrations (PK) ^p	X ^o	X	X	X			X			X			X	
Urine pregnancy test ^q (local; WCBP only)	X	X	X	X	X	X	X	X	X	X	X	X	X	X

Procedure ^a	Treatment Period (Visits 15-21, every-16-week visits)							ETV ^r	Follow-up Period (Visits 801 and 802)	
	Visit Number	V15	V16	V17	V18	V19	V20		V21	V801
Week Relative to Study Drug Initiation	120	136	152	168	184	200	208		LV +4W	LV +12W
Day Relative to Study Drug Initiation, with Visit Tolerance Interval	841 ± 5	953 ± 5	1065 ± 5	1177 ± 5	1289 ± 5	1401 ± 5	1457 ± 5		29 ± 5	85 ± 5
Physical examination ^c								X		X
Weight							X	X		
Concomitant medications	X	X	X	X	X	X	X	X	X	X
Adverse events	X	X	X	X	X	X	X	X	X	X
Vital signs (BP, temperature, and heart rate) ^d	X	X	X	X	X	X	X	X	X	X
PPD/Quantiferon-TB Gold/ T-SPOT.TB [®] (per local guidelines) ^e	TB testing required only based on clinical assessment of TB risk (symptoms/signs/known or suspected TB exposure), and according to local regulations and/or local standard of care.									
ECG ^f								X		X
C-SSRS	X	X	X	X	X	X	X	X	X	X
Self-Harm Supplement Form ^g	X	X	X	X	X	X	X	X	X	X
Self-Harm Follow-up Form	X	X	X	X	X	X	X	X	X	X
QIDS-SR16 (patient completed)	X	X	X	X	X	X	X	X		X
IP dispensed	X	X	X	X	X	X	X			
IP returned	X	X	X	X	X	X	X	X	X	
Investigator-Completed Clinical Efficacy Scales										
PASI	X	X	X	X	X	X	X	X	X	X
BSA	X	X	X	X	X	X	X	X	X	X
sPGA	X	X	X	X	X	X	X	X	X	X
PSSI ⁱ	X	X	X	X	X	X	X	X	X	X
NAPSI ⁱ	X	X	X	X	X	X	X	X	X	X

Procedure ^a	Treatment Period (Visits 15-21, every-16-week visits)							ETV ^r	Follow-up Period (Visits 801 and 802)	
	Visit Number	V15	V16	V17	V18	V19	V20		V21	V801
Week Relative to Study Drug Initiation	120	136	152	168	184	200	208		LV +4W	LV +12W
Day Relative to Study Drug Initiation, with Visit Tolerance Interval	841 ± 5	953 ± 5	1065 ± 5	1177 ± 5	1289 ± 5	1401 ± 5	1457 ± 5		29 ± 5	85 ± 5
PPASI ⁱ	X	X	X	X	X	X	X	X	X	X
Patient-Completed Health Outcomes Scales^j										
PSS	X	X	X	X	X	X	X	X		X
DLQI	X	X	X	X	X	X	X	X		X
Laboratory Tests										
Hematology ^k	X	X	X	X	X	X	X	X	X	X
Clinical Serum chemistry ^k	X	X	X	X	X	X	X	X	X	X
Urinalysis									X ^s	X
HsCRP	X	X	X	X	X	X	X	X	X	X
HBV DNA testing ^l	X	X	X	X	X	X	X	X	X	X
HCV RNA testing	X ^m	X ^m	X ^m	X ^m	X ^m	X ^m	X ^m	X ^m	X ^m	X ^m
Immunogenicity for mirikizumab ⁿ	X		X		X		X			X
Serum for mirikizumab concentrations (PK) ^p	X		X		X		X			X
Urine pregnancy test ^q (local; WCBP only)	X	X	X	X	X	X	X	X		X

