Therefore, based on all the available clinical and non-clinical data, the dosing regimens planned for this study are expected to provide an acceptable safety profile while providing maximum clinical response in patients with plaque psoriasis.

6. Study Population

The study population for Study AMAH will include patients who have completed participation in qualifying study periods of 1 of the originating studies (Study AMAF, AMAJ, AMAK, or AMBK) and meet eligibility criteria for Study AMAH, and will therefore include adult patients with moderate-to-severe plaque psoriasis at the time of entry into the originating study. Prospective approval of protocol deviations to recruitment and enrollment criteria, also known as protocol waivers or exemptions, are not permitted.

Patients in the secukinumab treatment group of Study AMAJ will be eligible to enter Study AMAH; such patients will receive mirikizumab for the first time in Study AMAH.

Approximately 1600-2000 patients are planned to be enrolled in Study AMAH.

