6.2. Exclusion Criteria

Patients will be excluded from study enrollment if they meet any of the following criteria, unless otherwise specified:

- [5] Have an unstable or uncontrolled illness, including, but not limited to, a cerebro-cardiovascular, respiratory, hepatic, renal, gastrointestinal, endocrine, hematologic, or neurologic disease, or abnormal laboratory values that developed during the originating mirikizumab study (Studies AMAF, AMAJ, AMAK, or AMBK) that, in the opinion of the investigator, would potentially affect patient safety within the study or would interfere with the interpretation of data.
- [6] Have a known hypersensitivity to mirikizumab or any component of this investigational product.
- [7] Have had investigational product permanently discontinued during a previous mirikizumab study.
- [8] Have had temporary investigational product interruption at any time during or at the final study visit of a previous mirikizumab study and, in the opinion of the investigator, restarting mirikizumab would pose an unacceptable risk for the patient's participation in the study.
- [9] Have any other condition that, in the opinion of the investigator, renders the patient unable to understand the nature, scope, and possible consequences of the study or precludes the patient from following and completing the protocol.
- [10] Are currently enrolled in any other clinical study involving an investigational product or any other type of medical research judged not to be scientifically or medically compatible with this study.

Other Exclusions

- [11] Are unsuitable for inclusion in the study in the opinion of the investigator or Sponsor for any reason that may compromise the patient's safety or confound data interpretation.

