10.3.6. Evaluation of Immunogenicity

Immunogenicity will be evaluated cumulatively, using data both from the patient's originating study and from the present study. Baseline for ADA assessment will be the baseline ADA assessment from the originating study, and postbaseline will be time after initiation of mirikizumab. The frequency and percentage of patients with preexisting (baseline) ADA and with treatment-emergent ADA to mirikizumab will be tabulated. For patients with treatment-emergent ADA, the frequency of neutralizing antibodies will also be tabulated.

The relationship between the presence of antibodies and the PK parameters and PD response, including safety and efficacy to mirikizumab, will be assessed.

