
Secondary
 
To evaluate the long-term efficacy and patient reported outcomes with mirikizumab treatment in patients with moderate-to-severe plaque psoriasis
	
Over the duration of the study:
 
 • Proportion of patients achieving sPGA (0,1) • Proportion of patients achieving PASI 90 • Proportion of patients achieving a 100% improvement in PASI (PASI 100) • Proportion of patients with a Psoriasis Symptoms Scale (PSS) symptom score of 0 (free of itch, pain, stinging, and burning) in those with a PSS symptoms score ≥ 1 at baseline. • Proportion of patients achieving a Dermatology Life Quality Index (DLQI) total score of (0,1) with at least a 5-point improvement (reduction) from baseline in patients with a baseline DLQI total score $\geq 5^*$ • Change in Palmoplantar Psoriasis Severity Index (PPASI) total score in patients with palmoplantar involvement at baseline* • Change in Psoriasis Scalp Severity Index (PSSI) total score in patients with scalp involvement at baseline* • Change in Nail Psoriasis Severity Index (NAPSI) total score in patients with fingernail involvement at baseline*

Objectives	Endpoints

Exploratory
 
To evaluate the potential development of anti-mirikizumab antibodies and their potential relationship with efficacy, TEAEs, and mirikizumab exposure
	
Over the course of the 208 week study, by treatment-emergent anti-drug antibody (TE-ADA) status and by neutralizing anti-drug antibody (NAb) status:
 
 • Relationship between ADA and efficacy (sPGA and PASI) • Relationship between ADA and TEAEs • Relationship between TE-ADA and mirikizumab pharmacokinetics

Abbreviations: ADA= antidrug antibodies; DLQI = Dermatology Life Quality Index; Nab = neutralizing anti-drug antibody; NAPSI = Nail Psoriasis Severity Index; PASI = Psoriasis Area and Severity Index; PPASI = Palmoplantar Psoriasis Severity Index; PSS = Psoriasis Symptoms Scale; PSSI = Psoriasis Scalp Severity Index; sPGA = static Physician’s Global Assessment; TE-ADA = treatment-emergent anti-drug antibody; TEAEs = treatment-emergent adverse events.

* Secondary objectives have been updated to align with a protocol amendment (a) to Study AMAK and protocol amendment (b) to Study AMAJ. Since Study AMAH has not had another protocol amendment, changes have been reflected in this SAP but differ from those listed in the Study AMAH protocol amendment (a).

5. Study Design

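### Relating ADA to outcomes by ever-positive TE-ADA status lets time in study bias the comparison: towards benefit for NRI or mNRI response, towards harm for crude TEAE counts

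*SAP*

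**What the plan says.** The exploratory objective (Protocol Table AMAH.2, SAP Table AMAH.4.1) covers ADA against sPGA and PASI, ADA against TEAEs, and TE-ADA against PK. All three are to be examined "Over the course of the 208 week study, by treatment-emergent anti-drug antibody (TE-ADA) status and by neutralizing anti-drug antibody (NAb) status".

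The only status rule is in SAP 6.12.2. It is a patient-level rule met "when at least one postbaseline ADA sample has a 4-fold increase in titer, compared to baseline", with a separate titer threshold for patients without ADA at baseline. One qualifying sample at any time is enough. The window is cumulative: "Immunogenicity will be evaluated cumulatively, using data both from the patient's originating study and from the present study" (Protocol 10.3.6, repeated in SAP 6.12.2). It opens with the first mirikizumab dose: "postbaseline will be time after initiation of mirikizumab". For patients who received secukinumab in AMAJ it opens only in AMAH, since "such patients will receive mirikizumab for the first time in Study AMAH" (Protocol Section 6, Study Population).

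In the Schedule of Activities, the row "Immunogenicity for mirikizumab" is marked at Weeks 0, 8, 16, 24, 48, 72, 96, 120, 152, 184 and 208 and at Visit 802. The early termination visit and Visit 801 are not marked.

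On outcomes, NRI counts a missing response as failure (SAP 6.3.3). mNRI, the SAP's primary method for categorical endpoints, does so only after discontinuation for an adverse event, death or lack of efficacy, and sends other discontinuations to multiple imputation (SAP 6.3.4). Protocol 10.3.4 tabulates TEAEs as numbers of patients. SAP 6.12.2 refers immunogenicity analyses to compound-level safety standards, and SAP 6.11 refers PK/PD to a separate plan.

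**The concern.** The number of chances to be labelled positive depends on how long a patient stays. A completer gives ten AMAH samples after Visit 1, plus Visit 802. A patient who leaves between Weeks 16 and 24 gives two, plus Visit 802 if attended. Under NRI, and partly under mNRI, leaving also counts as non-response. So the same event, dropout, lowers both the response rate and the chance of a positive label. Patients who seroconvert late have, by construction, stayed until late. This is immortal-time bias.

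The objective is there to show whether antibodies go with loss of efficacy, more adverse events or lower drug levels. An ever/never split can hide a real loss of response or invent a benefit. Longer follow-up also raises the chance of at least one TEAE, so the same split can invent a safety signal. For PK, concentrations measured before any antibody existed would be filed under the positive group.

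**Working it through.** The documents give no figure for TE-ADA incidence, AMAH dropout or adverse event rate, so there is no plan figure to reproduce and every rate below is an assumption. In all cases seroconversion is independent of response, dropout and adverse events. The true ADA effect is zero, and any gap is bias.

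**Check by hand.** Assume 40% discontinue over 4 years regardless of response, 10% are TE-ADA positive at AMAH entry, new seroconversion is λ = 0.05 per year, and 85% of stayers respond at Week 208. For simplicity, status is known up to the day of leaving.

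1. Dropout hazard: δ = −ln(0.60)/4 = 0.1277 per year.
2. Ever positive among completers: 0.10 + 0.90 × (1 − e^(−0.20)) = 0.10 + 0.90 × 0.1813 = 0.263.
3. New seroconversion among leavers: 1 − [δ/(δ+λ)] × (1 − e^(−4(δ+λ)))/0.40 = 0.086. Ever positive: 0.10 + 0.90 × 0.086 = 0.177.
4. Share completing, ever positive: 0.60 × 0.263 / (0.60 × 0.263 + 0.40 × 0.177) = 0.690.
5. Share completing, never positive: 0.60 × 0.737 / (0.60 × 0.737 + 0.40 × 0.823) = 0.573.
6. Week 208 NRI response: 0.85 × 0.690 = 58.7% against 0.85 × 0.573 = 48.7%. The spurious gap is about +9.9 points.

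A simulation of the same case that adds the Visit 802 sample for everyone gives 58.4% against 48.6% (+9.8). If half of dropouts count as failures and the rest are imputed at their true status, the gap halves to about +4.9. If all seroconversion precedes entry (λ = 0), steps 2 and 3 give the same value and the gap is zero.

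Crude TEAE incidence in that case, at 0.5 events per patient-year, is 78.0% in ever-positive and 71.7% in never-positive patients. The gap is +6.3 points towards harm.

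**Simulation with dropout linked to response.** This used 400,000 patients per setting, the AMAH sampling weeks and 80% stable responders. Yearly dropout was 5% in responders and 25% in non-responders with onset at 3% or 6% per year, or 8% and 15% with onset at 3%. Visit 802 attendance ran from 0 to 100%. The table gives Week 208 gaps, ever minus never positive, in points:

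| Positive at AMAH entry | NRI | mNRI, half of dropouts failing | As observed |
|---|---|---|---|
| 0% | +12 to +16 | +7 to +12 | about 0 |
| 10% | +6 to +11 | +4 to +8 | about 0 |
| 20% | +4 to +8 | +2 to +6 | about 0 |

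As-observed response at Week 48, grouped by status learned later, shows 0 to about +4 points.

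**Wider grid with dropout unrelated to response.** With 20% or 40% discontinuing over 4 years, onset of 2% to 10% per year, 0% to 20% positive at entry and full Visit 802 attendance, the NRI gap runs from +2.3 to +16.9. The crude TEAE gap runs from +1.2 to +11.0.

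**Does the alternative work?** Grouping by status known at AMAH Week 0 gives −0.4 to +0.2 points in the wider grid. A Week 48 landmark with later dropouts kept is within 0.6 points of zero in the response-linked settings. Both are simulation noise.

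**The case against.** The strongest reply is that the criticised comparison is not written down. SAP 6.12.2 commits to a definition and a status summary, for which cumulative status is right. The method for relating ADA to outcomes is left to compound-level standards and a PK/PD plan that are not available here, and may already use time-updated status. A reader might infer that a patient first positive at Week 152 is certain to be counted as positive for efficacy at Week 8. The documents do not say so. But the objective is worded by TE-ADA status, and the cumulative label is the only TE-ADA status defined, so it is the natural reading.

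A reader might also infer that TE-ADA will always look favourable, with a gap of around 15 points. That is not supported. Crude TEAE counts move the other way. As-observed response at Week 208 shows no gap. The largest figures need nobody positive at entry, although most AMAJ and AMAK patients enter after 52 weeks there. They also use NRI rather than mNRI, and low attendance at Visit 802, which all patients are meant to reach.

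A third tempting reading is that the exclusion of patients who "Have had investigational product permanently discontinued during a previous mirikizumab study" biases the comparison by leaving only survivors. Completing an originator period is the entry condition and the analysis population is AMAH ITT. Since every AMAH patient completed that period, dropout before entry does not create the gap.

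Finally, the objective is exploratory and nothing is tested. That limits the weight of the point but does not remove the bias from the estimate.

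**Conclusion.** The point holds in a limited form. Ever/never TE-ADA grouping can make antibodies look beneficial for NRI or mNRI response under no effect, can mask a true loss of a similar size, and can make them look harmful on crude TEAE counts. In the response-linked settings the spurious Week 208 gap is about +4 to +16 points by NRI and +2 to +12 by mNRI with half of dropouts failing. The position within each range depends mainly on prevalence at AMAH entry, seroconversion during AMAH and Visit 802 attendance. The bias vanishes if seroconversion is complete before entry. None of these rates is in the documents, so the direction for each type of outcome is firmer than the size. This is a cheap improvement to an exploratory analysis and does not affect the primary objective.

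**What to change.** In SAP 6.12.2:

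- **Incidence:** keep cumulative TE-ADA and NAb status for this table.
- **Efficacy:** classify patients by TE-ADA/NAb status known at a landmark (AMAH Week 0 and, for example, Weeks 24, 48, 96 and 152) among those in the study at that landmark. Compare later response with the planned mNRI and NRI handling, so that later dropouts stay in. Status updated at each visit is an alternative. If it is limited to patients still observed, it carries the caveat that SAP 6.3.1 attaches to as-observed analysis, and it loses patients who left after an antibody-related loss of response.
- **PK:** use status at the time of the sample.
- **TEAEs:** report rates per patient-time before and after first TE-ADA detection, with never-positive patients contributing to the time without detected TE-ADA.
- **Prior treatment:** tabulate by it, because the postbaseline window differs. Former secukinumab patients have no postbaseline sample at Week 0.
- **Deferred method:** if the compound-level standards already specify such an approach, cite it here.

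All data are already scheduled for collection. The cost is SAP wording, modest extra programming and smaller TE-ADA-positive groups at the early landmarks.
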